**D) Definition of Variables**

- a. **Outcome Variables:** Visual Analog Scale for pain intensity, Short-Form 36, Oswestry Disability Scale, Tolerable sitting time, wound complications, intra-operative complications
- b. **Independent Variables:** Age, gender, co-morbidities, type of coccygeal morphology
- c. **Potential Confounding Variables:** Disability status, pain medications prescribed by other physicians, co-existing musculoskeletal disease.

**E) Methodology:**

a. **Method of data collection:** A third party will meet with the patient at all data collection time points at the spine specialty clinic. Those patients who do not return as scheduled will be contacted by phone at which time either a phone interview will be conducted or the questionnaire will be mailed to the patient for completion.

### *Coccygectomy*

The surgical procedure will be performed at a tertiary care center in an operating room suite. Pre-operatively, patients will complete a dulcolax suppository and will receive pre-operative dose of first generation cephalosporin, vancomycin, or clindamycin for antibiotics. Patients will be placed under general anesthesia and positioned in knee-to-chest position. An incision will be made directly over the coccyx and cautery dissection will be used to identify the terminal mobile segment. The mobile segment will be removed and will be sent for pathology. The wound will be irrigated and closed in two layers with dermabond placed over the incision. Patients will be discharged home the day of surgery if appropriate. Postoperatively, patients will be placed on milk of magnesia and will sit in a donut cushion seat until seen at clinic follow-up two weeks post-operatively.

### *Visual Analog Pain Scale*

Visual analog scales (VAS) are one of the most frequently used measurement scales in health care research. A Visual Analogue Scale (Figure 3) is a measurement instrument that tries to measure a characteristic or attitude that is believed to range across a continuum of values and cannot easily be directly measured. For example, the amount of pain that a patient feels ranges across a continuum from none to an extreme amount of pain. From the patient's perspective this spectrum appears continuous ± their pain does not take discrete jumps, as a categorization of none, mild, moderate and severe would suggest. It was to capture this idea of an underlying continuum that the VAS was devised. Operationally a VAS is usually a horizontal line, 100 mm in length, anchored by word descriptors at each end, as illustrated in Fig. 3. The patient marks on the line the point that they feel represents their perception of their current state. The VAS score is determined by measuring in millimeters from the left hand end of the line to the point that the patient marks. There are many other ways in which VAS have been presented, including vertical lines and lines with extra descriptors. As such an assessment is clearly highly subjective, these scales are of most value when looking at change within individuals, and are of less value for comparing across a group of individuals at one time point. It could be argued that a VAS is trying to produce interval/ratio data out of subjective values that are at best ordinal. Thus, some caution is required in handling such data. Many researchers prefer to use a method of analysis that is based on the rank ordering of scores rather than their exact values, to avoid reading too much into the precise VAS score.

### *Short-Form 36*

A 36-item short-form (SF-36) was constructed to survey health status in the Medical Outcomes Study. The SF-36 (Figure 4) was designed for use in clinical practice and research, health policy evaluations, and general population surveys. The SF-36 includes one multi-item scale that assesses eight health concepts: 1) limitations in physical activities because of health problems; 2) limitations in social activities because of physical or emotional problems; 3) limitations in usual role activities because of physical health problems; 4) bodily pain; 5) general mental health (psychological distress and

well-being); 6) limitations in usual role activities because of emotional problems; 7) vitality (energy and fatigue); and 8) general health perceptions.

#### *Tolerable Sitting Time*

Patients will be asked how long they can sit before pain and discomfort forces them to stand. This data can help isolate the change in mechanical pain associated with coccygodynia following treatment. Patients will complete this item at every clinic visit (Figure 6).

#### *Oswestry Disability Scale*

The Oswestry Disability Index (ODI) has become one of the principal condition specific outcome measures used in the management of spinal disorders (Figure 5). Fairbank et al confirmed its validity and reliability and is considered gold standard outcome measure (4).

#### *Radiographs*

Sitting and standing lateral radiographs will be obtained on all patients enrolled in the study. The Maigne criteria will be used to detect any abnormalities (figure 2).

- B) Control Patients:** There will be no true control group.
- C) Projected study duration:** 3 years. Patients will be enrolled for a two year period and all patients will have at least a 24 month follow-up.

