**Study Design**

**A) Summary of Study Design:**

All patients will be seen and enrolled through an outpatient spine specialty clinic of the senior author. Patients that meet the inclusion criteria will be offered enrollment in the study by a third party (clinical research assistant). Patients enrolled will then complete pre-treatment SF-36, Oswestry Disability Scale and a pain visual analog scale. Patients will be followed at 2 weeks, 6 weeks, 3 months, 6 months, 1 year and 2 years after treatment. Patients will complete the

questionnaire containing the VAS and tolerable sitting time at all visits with SF-36 and Oswestry disability scale completed at one year post treatment.

**B) Type of Study:** Prospective Observational Study

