#### *Sample Size*

As the scale of measurement for the VAS, SF-36, and the Oswestry Disability Scale are all on the ordinal scale, the Wilcoxon rank sum test will be used to compare the two groups. The sample size for the Wilcoxon rank sum test was calculated using the formulas derived by Noether. Forty-four people are needed in each group to insure a power of 90%, with an alpha of 0.05, and  $p'' = \text{probability}(Y > X) = 0.70$  where Y and X are random samples from two populations. Under the null hypothesis  $p'' = 0.50$ . To allow for lost to follow-up, fifty subjects will be recruited for each arm of the trial.

Sample size is predicted to be achieved within two years, estimating a yearly enrollment of 50 patients

[figure not shown]

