## **Feasibility of Project**

- A) Time frame: 3 years
- B) Budget:**
  - a. Patients will be compensated \$50 each for completion of the study- \$5000. Patients will be paid \$20 at the first follow-up appointment and an additional \$30 at the final follow-up if their data set is complete.
  - b. SF-36 licensing fees: \$500 for 2 years.
  - c. Total- \$5,500
- C) **Available population:** Senior author is a major referral physician for coccygodynia. Expect to enroll 50 patients per year for 2 years. Previous treatments will be recorded to further characterize the study population and to determine its applicability to the general population of patients with this condition.
- D) **Equipment:** none

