### Coccygodynia Questionnaire

To be completed at enrollment, 2 weeks, 6 weeks, 3 months, 6 months and 1 year after treatment

Date of Treatment \_\_\_\_\_  
Today's Date \_\_\_\_\_

Pt name \_\_\_\_\_  
MRN \_\_\_\_\_

1. Please draw a vertical mark (like this: |) on the line below, which best describes the amount of pain you feel where your tailbone is or was.

2. What medicines are you currently taking to control or treat pain at the site where your tailbone is or was? Please include the dose and how often you take the medicine.

3. Are you taking the medicines you have listed above in question 2 every day? For each medicine listed in your response to question 2, please write YES or NO.

4. Please check the most appropriate box for you regarding sitting.

- I can sit in any chair as long as I like.
- I can only sit in my favorite chair as long as I like.
- Pain prevents me from sitting more than 1 hour.
- Pain prevents me from sitting more than 0.5 hours.
- Pain prevents me from sitting more than 10 minutes.
- Pain prevents me from sitting at all.

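### The 3-year study duration is 12 months too short for two-year enrolment plus 24 months of follow-up, and the questionnaire header omits the 2-year visit

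*Combined protocol and SAP*

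**What the plan says.** **Duration.** Item C) Projected study duration, which follows the Radiographs text, gives 3 years and then states: "Patients will be enrolled for a two year period and all patients will have at least a 24 month follow-up". Feasibility of Project repeats the total: "Time frame: 3 years".

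**Enrolment.** The two-year window appears twice more. Sample Size says "Sample size is predicted to be achieved within two years, estimating a yearly enrollment of 50 patients", and Feasibility of Project says "Expect to enroll 50 patients per year for 2 years". The budget there is $5,000 at $50 per patient.

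**Visits.** The Summary of Study Design says "Patients will be followed at 2 weeks, 6 weeks, 3 months, 6 months, 1 year and 2 years after treatment". It calls for the "questionnaire containing the VAS and tolerable sitting time at all visits" and places the post-treatment SF-36 and Oswestry scale at one year. The Tolerable Sitting Time section also asks for the sitting item at each clinic visit and points to Figure 6.

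**The form.** Figure 6, the Coccygodynia Questionnaire, is headed: "To be completed at enrollment, 2 weeks, 6 weeks, 3 months, 6 months and 1 year after treatment". It has no 2-year time point.

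**The concern.** A total duration has to cover the enrolment window plus the follow-up of the last patient enrolled. Here the total is shorter than that sum, so a stated planning figure cannot be delivered by the stated design. Anything scheduled from the 3-year figure would end a year early.

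The form matters more directly for the data. The Summary of Study Design places the SF-36 and ODI at one year, so the Coccygodynia Questionnaire is the only questionnaire it schedules at 2 years. If staff work from the header, the 2-year visit yields no VAS and no sitting time. Both are listed outcome variables, and both appear in the first null hypothesis.

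Both discrepancies raise the same question: whether the 2-year visit is part of the study.

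**Working it through.** **Inputs**

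| Quantity | Value | Where stated |
|---|---|---|
| Total duration | 3 years = 36 months | Projected study duration; Feasibility of Project |
| Enrolment window | 2 years = 24 months | Projected study duration; Sample Size; Feasibility of Project |
| Minimum follow-up, every patient | 24 months | Projected study duration; last visit in Summary of Study Design |
| Accrual rate | 50 per year | Sample Size; Feasibility of Project |
| Patient payments | $5,000 at $50 each | Feasibility of Project, Budget |

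**Step 1. Can the stated 36 months be reproduced?** Minimum duration = enrolment window + follow-up of the last patient enrolled.

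- 24 months of enrolment + 12 months of follow-up = 36.
- 12 months of enrolment + 24 months of follow-up = 36.

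Each of these changes one of the plan's own inputs. No combination that keeps both inputs gives 36.

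**Step 2. Is the two-year window itself a slip?** The budget implies $5,000 / $50 = 100 patients. At 50 per year, 100 / 50 = 2 years. The window agrees with the budget and the accrual rate.

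**Step 3. Duration from the stated inputs.** 24 + 24 = 48 months. The shortfall is 48 − 36 = 12 months. This is a minimum, because visits are timed from treatment, so any wait between enrolment and surgery adds to it.

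**Step 4. What a stop at month 36 would mean.** No part of the document says data collection stops then, so this is conditional only. The last patient enrolled would have 36 − 24 = 12 months of follow-up. Only patients enrolled by month 36 − 24 = 12 could reach 24 months. With even accrual of 100 patients and no delay to surgery, that is 100 × 12/24 = 50 patients.

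**Step 5. The form against the visit schedule.**

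| Post-treatment time point | Summary of Study Design | Questionnaire header |
|---|---|---|
| 2 weeks | yes | yes |
| 6 weeks | yes | yes |
| 3 months | yes | yes |
| 6 months | yes | yes |
| 1 year | yes | yes |
| 2 years | yes | **no** |

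The header covers 5 of the 6 post-treatment time points. It is a complete sentence, so the gap does not come from text lost when the PDF was read.

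**The case against.** The other side accepts the arithmetic and contests its weight.

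- **Little depends on the 3-year figure.** The patient payments are per head, no test is tied to month 24 or month 36, and nothing says collection stops at month 36. Taken alone, the duration error is close to an editorial correction. This is fair, and the figure of 50 in 100 should carry no weight in judging how serious the point is.
- **The header need not override the protocol.** The study design requires the form at all visits, a third party collects data at every time point with telephone or mail as backup, and the last $30 is paid only for a complete data set. This stands in part: loss of the 2-year data is a risk if the header is followed, not a certainty. But the form and the design still disagree on when the last questionnaire is due, which also leaves unclear what counts as complete for the payment.
- **The error may lie elsewhere.** Two years of enrolment plus a 1-year final visit gives exactly 36 months. The form stops at 1 year, and so do the SF-36 and ODI. A 2-year visit that was not carried through every section would explain all of this. That is a reasonable inference, but the document does not say so, and it states the 2-year visit and the 24-month minimum explicitly. The sponsor has to confirm which was intended.

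Collecting follow-up by telephone or mail does not remove the conflict. It changes how a patient is contacted, not the date on which 24 months is reached.

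**Conclusion.** The concern holds on both counts. The stated design needs at least 48 months and the plan gives 36, so the projected duration is at least 12 months short. The questionnaire header omits one of the six post-treatment time points, the one at 2 years. The first result rests only on the plan's own enrolment window and minimum follow-up, and the second on a direct comparison of two lists. Neither needs an outside figure.

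The plain reading is a wrong calendar total, not a planned truncation of follow-up. The 1-year SF-36 and ODI and the 44 per group are not put in question. The point should be fixed, chiefly because the form is what staff will have in hand at the visits.

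**What to change.** **Main correction.** State the duration as at least 4 years, ending at the last patient's 2-year visit, in both Projected study duration and Feasibility of Project. Add the 2-year time point to the Coccygodynia Questionnaire header. This keeps the enrolment window, follow-up and visits as written. The cost is a change of wording in two places and one entry on the form, with no new patients and no visits beyond those already listed. If the sponsor had in fact planned and resourced only 3 years, the extra year has a real cost, which the document does not give.

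**If 3 years is intended,** another stated element must change consistently in the Summary of Study Design, Projected study duration, Sample Size, Feasibility of Project and the form:

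- *Final visit at 1 year* (24 + 12 = 36 months). The 2-year visit and the 24-month minimum are withdrawn, and the 2-year VAS and sitting time are given up.
- *Enrolment over 12 months* (12 + 24 = 36 months). At 50 per year this gives 50 patients, half of the 100 budgeted. Payments become 50 × $50 = $2,500, and the total becomes $2,500 + $500 = $3,000 instead of $5,500, if the licence fee is unchanged. The 2-year time point must still be added to the form. The sponsor must also say whether the target of fifty per arm means 50 or 100 people, because the analysis section defines the two groups as pre- and post-operative.

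**Side check.** The SF-36 licence is budgeted for 2 years. With two-year enrolment and a 1-year SF-36, use spans 24 + 12 = 36 months. The licence terms are not given, so the sponsor should confirm that the line is sufficient.

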#### **Statistical Procedures for Analysis and Sample Size Determination**

Standard statistical tests will be used. Descriptive statistics including means and standard deviations, or counts and percentages will be reported. As the scale of measurement for the VAS, SF-36, and the Oswestry Disability Scale are all on the ordinal scale, the Wilcoxon rank sum test will be used to compare the two groups (pre- and post-operative). Complication rates will be calculated.

A p-value of less than 0.05 will be considered statistically significant. The SAS software will be used for all analyses.

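### One cohort's pre- and post-operative scores are tested and sized as two independent groups (Wilcoxon rank sum), which does not fit the paired design

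*Combined protocol and SAP*

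**What the plan says.** All references are to the combined protocol and SAP.

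- **Statistical Procedures for Analysis and Sample Size Determination.** For VAS, SF-36 and Oswestry, "the Wilcoxon rank sum test will be used to compare the two groups (pre- and post-operative"). No other test is named, and neither the visit nor the patients entering the comparison are specified.
- **Sample Size.** The same test is sized by Noether's method for 90% power, alpha 0.05 and P(Y > X) = 0.70, "where Y and X are random samples from two populations". This gives 44 per group, and to cover losses "fifty subjects will be recruited for each arm of the trial".
- **Control Patients** (after Radiographs). "There will be no true control group".
- **Summary of Study Design.** Enrolled patients complete SF-36, Oswestry and VAS before treatment. Afterwards the same patients complete the "questionnaire containing the VAS and tolerable sitting time at all visits with SF-36 and Oswestry disability scale completed at one year post treatment".
- **Visual Analog Pain Scale.** On VAS scores, "these scales are of most value when looking at change within individuals, and are of less value for comparing across a group of individuals". The sentence goes on to limit that contrast to a single time point.

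No paired method, pre/post correlation or standard deviation of change appears anywhere.

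**The concern.** The rank sum test assumes two independent samples. Here the two groups are the same people measured twice, so the standard error behind the p-value ignores the covariance between a patient's two scores. If that covariance is positive, the test overstates the variability of the change, p-values are too large, and small changes are harder to detect.

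The same assumption shapes the sample size. There are no arms, and one patient supplies both a pre- and a post-operative score, so a count per group that is then doubled does not describe this cohort.

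An unpaired test also needs no matched scores. If all available data were used, baselines of patients who never returned could be set against follow-up scores of those who did, mixing loss to follow-up with change after surgery.

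**Working it through.** **1. The plan's own figure.** Inputs from Sample Size: alpha 0.05 (sidedness not stated), power 90%, P(Y > X) = 0.70. Noether's two-sample formula with equal groups gives, per group,

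n = (1.960 + 1.282)² / (6 × 0.20²) = 43.8, rounded up to 44.

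This matches when alpha is two-sided; one-sided would give 36. The parameter, the two populations, the per-group count and the arms all belong to the independent-samples test.

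**2. Number of pairs.** The plan recruits 50 + 50 = 100 patients. Its loss allowance is 1 − 44/50 = 12%, which leaves 88 patients with both scores.

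**3. Effect on a common scale.** Under assumed normality with equal variances, P(Y > X) = 0.70 is a shift of √2 × 0.524 = 0.74 SD.

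**4. Behaviour of the tests on paired data.** The correlation r is an assumption, shown over a range. Simulation used 88 bivariate normal pairs, two-sided 0.05, with 40,000 replicates for size and 20,000 for power. Pairs needed come from these formulas:

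- Signed-rank: N = (1.960 + 1.282)² / [3(p − 0.5)²], where p is the probability that two patients' changes sum to a positive value, Φ(0.742/√(1 − r)). For r = 0, 0.3, 0.5, 0.7, p = 0.771, 0.812, 0.853, 0.912 and N = 47.7, 35.9, 28.1, 20.6. Simulation needs slightly fewer (about 43, 30, 23, 14).
- Sign test: exact binomial, with within-patient P(Y > X) = 0.700, 0.735, 0.771, 0.831.

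| r | Rank sum true type I error | Power at 0.3 SD: rank sum / signed-rank / sign | Pairs for 90% power at 0.74 SD: signed-rank / sign |
|---|---|---|---|
| 0 | 4.9% | 49 / 48 / 33% | 48 / 70 |
| 0.3 | 2.1% | 48 / 63 / 44% | 36 / 49 |
| 0.5 | 0.7% | 48 / 77 / 57% | 29 / 37 |
| 0.7 | 0.1% or less | 48 / 94 / 80% | 21 / 23 |

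The signed-rank test held 4.9% to 5.0% and the sign test 4.1% to 4.3% at every r. With six equally likely categories, like the sitting item, rank sum size was 5.2, 2.2, 0.8 and 0.1%, while signed-rank held 5.0% to 5.2%.

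**5. Larger changes.** At an assumed 0.5 SD, power for rank sum / signed-rank / sign is 93 / 97 / 86% (r = 0.3), 96 / 99 / 95% (0.5) and 99 / >99 / >99% (0.7). At the planned 0.74 SD it is above 99%, above 99% and at least 97%.

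**6. Outside that range.** At r = −0.2 rank sum size rises to about 7.1%, and the need becomes 56 pairs (signed-rank) or 81 (sign test). With the post-operative SD half the baseline SD, rank sum size is about 6% at r = 0 and about 3.4% at r = 0.3.

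**The case against.** The strongest defence is that the error does little harm. With positive correlation it is conservative and does not manufacture a benefit. At the only effect the plan states, power is above 99%, and the planned recruitment is ample. The material power loss appears at 0.3 SD, a value the plan never names, and even at 0.5 SD the rank sum test keeps 93% to 99%. All of this stands, and it limits the seriousness. It does not make the p-values of the only named test correct.

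The conservative direction is itself conditional: step 6 shows type I error above 5% with negative correlation, or with zero correlation and unequal variances. That limits the reassurance, but it is a further reason to pair. Likewise, r = 0 gives the largest sample need only among non-negative correlations; at −0.2 the need is still below 88 pairs.

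The VAS passage contrasts change within patients with comparison between patients at one time point, so it does not directly rule out a group-level pre/post comparison. Its first half still favours analysing each patient's change.

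A paired test does not remove bias from loss to follow-up. It makes the comparison like for like and shows how many patients are missing. Restoring each test to 5% also leaves about 11 comparisons (VAS, Oswestry, eight SF-36 scales, sitting time) without a multiplicity rule. That is a separate matter, and miscalibrated p-values are no remedy for it.

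**Conclusion.** The concern holds. Both the test and the sample size assume independent groups that the design does not have. This should be fixed, but it does not threaten the study: for non-negative correlation and equal variances the test is conservative, with true size falling from 4.9% to 0.1% or less as r goes from 0 to 0.7. The practical loss is confined to changes well below the planned one. The 88 expected pairs exceed every requirement in the table, the largest being 70.

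These sizes rest on assumed bivariate normal scores, on correlations the documents do not give, and on reading 0.70 as the two-sample probability the plan defines. Read instead as the signed-rank probability it would need 10.51/(3 × 0.04), or 88 pairs; as the sign-test probability, 10.51/(4 × 0.04), or 66 by the normal approximation. Neither exceeds 88.

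**What to change.** **Analysis section.** Replace the rank sum test with a paired test of each patient's score at a named visit against that patient's own baseline. One year is a workable example: SF-36 and Oswestry are collected then, and the VAS and sitting questionnaire is marked "To be completed at enrollment, 2 weeks, 6 weeks, 3 months, 6 months and 1 year after treatment".

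- For VAS, Oswestry and each SF-36 scale, use the Wilcoxon signed-rank test and report the Hodges-Lehmann estimate of change with a 95% confidence interval.
- The signed-rank test ranks the sizes of differences. The protocol says a VAS may be "trying to produce interval/ratio data out of subjective values that are at best ordinal". If the sponsor holds to that view, use the sign test and accept its lower power.
- Apply a paired test to the sitting item as well. The first null hypothesis names it, but the analysis section does not list it.
- State that patients with both scores enter each test, and report how many do not.

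**Sample Size section.** Replace the counts per group and per arm with one cohort of pairs, stating the assumed shift and correlation. For 90% power at 0.74 SD and r = 0, this is 48 pairs (signed-rank) or 70 (sign test). The planned 100 patients, or 88 pairs after 12% loss, cover either.

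**Cost.** Revised wording in two sections and a short recalculation, with no new patients, visits, data or software. If the sign test is chosen, its power at 0.3 SD is below that of the rank sum test at low correlation (for example 44% against 48% at r = 0.3).

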**Null Hypotheses:**

1. Coccygectomy will not improve scores on the SF-36, ODI, tolerable sitting time, or VAS.
2. There are no independent variables associated with improved outcomes.

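### No primary outcome, no post-operative visit for VAS and sitting time, and no multiplicity rule: roughly an even chance of a false predictor, and an uncontrolled but smaller chance of a false improvement claim

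*Combined protocol and SAP*

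**What the plan says.** **Hypotheses.** Null Hypothesis 1 reads "Coccygectomy will not improve scores on the SF-36, ODI, tolerable sitting time, or VAS". The four instruments are joined without ranking. Null Hypothesis 2 reads "There are no independent variables associated with improved outcomes", so one significant association with any outcome would reject it. Definition of Variables lists four independent variables: age, gender, co-morbidities and type of coccygeal morphology.

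**Visits.** Summary of Study Design states "Patients will be followed at 2 weeks, 6 weeks, 3 months, 6 months, 1 year and 2 years after treatment", and that patients complete the "questionnaire containing the VAS and tolerable sitting time at all visits with SF-36 and Oswestry disability scale completed at one year post treatment". VAS and sitting time therefore have six post-operative values each, while SF-36 and Oswestry have one. The Coccygodynia Questionnaire form carries a different schedule, "To be completed at enrollment, 2 weeks, 6 weeks, 3 months, 6 months and 1 year after treatment", with no 2-year entry.

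**SF-36.** It is described as "one multi-item scale that assesses eight health concepts". No scale or summary score is chosen for analysis.

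**Analysis.** For VAS, SF-36 and Oswestry, "the Wilcoxon rank sum test will be used to compare the two groups (pre- and post-operative". The post-operative visit is not named, and sitting time is not listed under this test. The only significance rule is "A p-value of less than 0.05 will be considered statistically significant". For predictors, the section offers only a general reference to standard tests.

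**The concern.** A 5% threshold limits the error of one pre-chosen test. Here either null hypothesis can be rejected on the most favourable of several tests, and for VAS and sitting time the visit can be chosen after the data are seen. Finding predictors is one of the study's two stated purposes, and the Summary says that the results should help guide clinicians. A chance predictor could then influence who is offered surgery. For the before/after comparison, a reader of the report could not tell a planned result from the best of several.

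**Working it through.** **1. The plan's own figure.** Noether's formula with equal groups: N = (z(alpha) + z(power))² / (12 × 0.25 × (0.70 − 0.50)²). With two-sided 0.05 and 90% power, N = (1.960 + 1.282)² / 0.12 = 87.56, so 44 per group, as stated. One-sided 0.05 gives 36, so the plan's alpha is two-sided. That calculation is for a single test.

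**2. How many tests the plan permits.**
- Before/after: VAS 6 + sitting time 6 + SF-36 concepts 8 + Oswestry 1 = 21. On the questionnaire form's schedule it is 5 + 5 + 8 + 1 = 19. With one test per instrument it is 4.
- Predictors: 4 variables × 4 instruments = 16. With eight SF-36 scales it is 4 × 11 = 44, and more if co-morbidities are split.

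**3. False predictor, all nulls true.** If the tests are independent, 1 − 0.95^16 = 56.0%. Next, let the four outcomes be equally correlated and the four predictors independent of each other. The chance of any false result for one predictor is q, and over four predictors it is 1 − (1 − q)^4.

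| Outcome correlation (assumed) | q, 4 outcomes | 16 tests |
|---|---|---|
| 0 | 18.5% | 56% |
| 0.3 | 17.4% | 53% |
| 0.5 | 15.6% | 49% |
| 0.7 | 13.0% | 43% |

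**4. False improvement, all nulls true.** Only the improvement direction counts, at 0.025 per test. For 21 independent tests, 1 − 0.975^21 = 41.2%; for 4 tests, 1 − 0.975^4 = 9.6%.

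The tests share a baseline and the same patients, so all 21 were also simulated together (88 patients, normal scores, 3,000 runs). The documents give no correlations, so those below are assumptions.

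| Correlation: pre/post; between post visits; between outcomes | Rank sum: error per test | Rank sum: any false improvement | Paired signed-rank: any false improvement |
|---|---|---|---|
| 0; 0; 0 | 5.0% | 36% | 37% |
| 0.3; 0.5; 0.3 | 2.2% | 15% | 28% |
| 0.5; 0.5; 0.3 | 0.7% | 7% | 31% |
| 0.5; 0.7; 0.5 | 0.7% | 5% | 23% |
| 0.7; 0.7; 0.5 | 0.1% | 0.5% | 27% |

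The rank sum test treats before and after scores as independent groups. On positively correlated pairs it rejects too rarely, which hides part of the multiplicity. A correct paired test, with nothing else changed, brings the error back to 23–37%.

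**5. Power after adjustment.** Expected enrollment is 50 per year for two years, and the budget ($5,000 at $50 each) also implies 100 patients. The plan's own allowance (44 of 50, or 88%) leaves 88 pairs. For normal scores, P(Y > X) = 0.70 corresponds to a shift of √2 × 0.524 = 0.742 SD. Signed-rank power (efficiency 3/π) at two-sided 0.0125 is 98.95% at zero pre/post correlation and 99.9% at 0.3. A direct simulation at zero correlation gave 98.5%.

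**The case against.** **The counts are a reading of the plan.** The analysis section does not say that every visit or every SF-36 scale will be tested, names no test for sitting time, and specifies no predictor test. This stands: 21 is the most that the before/after wording permits, and 4 is a fair minimum.

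**The visit is not open for everything.** SF-36 and Oswestry have only the one-year follow-up. This also stands, so the freedom to choose a visit is confined to VAS and sitting time.

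**A false claim that surgery helps is not shown to be likely.** A reader might compute 1 − 0.95^21 = 66% and infer that it is. That figure counts significant worsening as well, takes the tests as independent, and gives each exactly 5% error. The planned rank sum test has about 2% error per test or less at pre/post correlations of 0.3 and above. Every figure also assumes no true change, whereas the plan assumes P(Y > X) = 0.70 and the surgical series in its Background report benefit in most patients. The stronger inference is therefore unsupported. The protection is nonetheless accidental, because it comes from using an unpaired test on paired data.

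**Adjustment does not make the comparison causal.** True: Control Patients states that there is no true control group. That is a separate limitation, which multiplicity control does not address.

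**Conclusion.** The concern holds in limited form. The plan names no primary outcome, no post-operative visit for VAS and sitting time, and no multiplicity rule, and 0.05 is its only threshold.

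The predictor aim is the more exposed. If no predictor has any effect, there is roughly an even chance of at least one false predictor (43–56% over 16 tests, for outcome correlations from 0.7 down to 0), and more if SF-36 scales or co-morbidities are split.

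The chance of a false improvement claim is uncontrolled but smaller. It is 41% if 21 tests were independent, about 5–15% with the planned rank sum test at assumed pre/post correlations of 0.3 to 0.5, and about 23–37% if a paired test is adopted without a primary outcome. These figures use the maximum of 21 tests; fewer tests would lower them.

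**What to change.** In Statistical Procedures for Analysis and Sample Size Determination:

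1. Name one primary outcome at one year, the only follow-up visit with all four instruments and one that appears in both schedules. VAS is one choice. Oswestry is another, since the protocol itself calls it the gold standard. The choice is the sponsor's.
2. Test it at two-sided 0.05 with a paired Wilcoxon signed-rank test, and state that this replaces the rank sum test. Do not change the test without also naming the primary outcome.
3. Let the decision on Null Hypothesis 1 rest on the primary outcome. If it is significant, test the other three instruments at one year, with one named SF-36 score, by Holm (0.05/3 = 0.0167, then 0.025, then 0.05).
4. Report other visits and other SF-36 scales as estimates with confidence intervals only.
5. Label the predictor analyses exploratory, or apply Holm to all predictor-by-outcome tests as one family (first step 0.05/16 = 0.0031). Holm within each outcome would leave four separate 5% families, up to 18.5% overall, and would not control Null Hypothesis 2.
6. Reconcile the visit schedules in Summary of Study Design and on the Coccygodynia Questionnaire form.

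The cost is a few sentences and a stricter threshold for secondary outcomes. With 88 pairs, power at the plan's effect stays about 99% even at 0.0125, which is stricter than Holm's first step. Adjusted predictor tests would lose more power. The loss cannot be sized, because the documents give no predictor effect, and the exploratory label avoids it.
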